10.2 Subject Accountability

The number of subjects screened, enrolled in lipid stabilization, randomized, received IP, and completed study will be summarized. Key study dates for the first subject enrolled, last subject enrolled and last subject's end of study will be presented.

Study discontinuation and IP discontinuation will be tabulated separately by reasons for discontinuation. This tabulation will include study discontinuations during the lipid stabilization period.

The number of subjects included in and excluded from each analysis set and reason for exclusion will also be summarized.

10.3 Important Protocol Deviations

Important Protocol Deviations (IPDs) categories are defined by the study team before the first subject's visit and updated during the IPD reviews throughout the study prior to database lock. These definitions of IPD categories, sub-category codes, and descriptions will be used during the course of the study.

Eligibility deviations are defined in the protocol.

10.4 Demographic and Baseline Characteristics

All baseline tables will be summarized by randomized treatment group and for all subjects in FAS. Baseline tables will summarize the following: baseline characteristics, demographics, cardiovascular medical history, laboratory parameters, and lipid-regulating concomitant medications.

Summary statistics for percent change from screening LDL-C to baseline LDL-C for subjects in the FAS will be provided.

10.5 Efficacy Analyses

The following table summarizes the key efficacy analyses that will be conducted:

Table 2.	Key	/ Efficacy	y Anal	yses	Summar	y Table
----------	-----	------------	--------	------	--------	---------

Endpoint	Statistical Analysis Method	P-values from the Statistical Tests	Hierarchical Testing Procedure for testing of Treatment Effect vs. Placebo. As specified in the Multiplicity Adjustment Method Diagram	
Co-primary Endpoints				
Mean percent change from baseline at weeks 10 and 12 in LDL-C	Repeated measures model	P1 = Maximum of the two p-values for the co-primary endpoint pair from	P1 compare to $\alpha = 0.05$	
Percent change from baseline at week 12 in LDL-C		the primary analysis		
Co-secondary Endpoints (Tier 1)				
Mean change from baseline at weeks 10 and 12 in LDL-C	Repeated measures model	For each lipid parameter,	If P1 < 0.05 → All P2a's from each lipid	
Change from baseline at week 12 in LDL-C		P2a = Maximum of the two p-values for each tier 1 co-secondary endpoint pair	parameter will be tested through Hochberg method with α = 0.005 Else (i.e. co-primary endpoint is not	
And			significant)	
Mean percent change from baseline at weeks 10 and 12 and			→ No further testing	
Percent change from baseline at week 12				
in each of the following lipid parameters:				
non-HDL-C, ApoB100, total cholesterol, total cholesterol/HDL-C ratio, and ApoB100/ApoA1 ratio				
And				

Page 1 of 2

Endpoint	Statistical Analysis Method	P-values from the Statistical Tests	Hierarchical Testing Procedure for testing of Treatment Effect vs. Placebo. As specified in the Multiplicity Adjustment Method Diagram
Mean achievement of LDL-C < 70 mg/dL at weeks 10 and 12	Cochran Mantel-Haenszel (CMH) test		
 Achievement of LDL-C < 70 mg/dL at week 12 			
Co-secondary Endpoints (Tier 2)			
Mean percent change from baseline at weeks 10 and 12	Repeated measures model	For each lipid parameter, P2b = Union-intersection test p-	If all P2a's are significant through Hochberg method
 Percent change from baseline at week 12 		value from the two contrasts of each tier 2 co-secondary endpoint pair	 All P2b's from each lipid parameter will be tested through Hochberg method with α = 0.025
in each of the following lipid parameters:			5
Lp(a), triglycerides, HDL-C, and VLDL-C			Else (i.e. one or more co-secondary endpoints (tier 1) is not significant) → All P2b's will be tested through Hochberg method with α = 0.02

Table 2. Key Efficacy Analyses Summary Table

Page 2 of 2

10.5.1 Analyses of Co-primary Endpoints

10.5.1.1 Primary Analysis of Co-primary Efficacy Endpoints

To assess the co-primary endpoints of the mean percent change from baseline in LDL-C at weeks 10 and 12 and the percent change from baseline in LDL-C at week 12, a repeated measures linear effects model will be used in each dose frequency to compare the efficacy of evolocumab in combination with atorvastatin and placebo in combination with atorvastatin in the FAS. The repeated measures model will include terms for treatment group, stratification factors (from IVRS/IWRS), scheduled visit and the interaction of treatment with scheduled visit. To account for the repeated LDL-C measurements within a subject across the visits, the repeated measures linear effects model will use an unstructured covariance (Littell, 2000). China and South Korea may be combined as one stratum if LS means estimates cannot be derived from the repeated measures model due to small sample size of South Korea. If there is still convergence issue due to sample size of China and South Korea, only the entry statin therapy stratification will be included in the model.

Multiplicity adjustment procedures are defined in Section 10.1.

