Vital signs, AEs/**ADEs**/SAEs, concomitant therapy, evaluation of fasting lipids, dietary instruction, physical exam, measuring waist circumference, body height and weight, 12-lead ECGs, other laboratory assessments, including assessment for anti-evolocumab antibodies, biomarker sample collection, serum pregnancy testing (females of childbearing potential), MMTT, urinalysis, and steroid analyte testing will be carried out per the Schedule of Assessment (Table 1) of the protocol. If the subject consented to pharmacogenetics analyses, deoxyribonucleic acid (DNA) will be extracted from some of the blood samples. IP administration by SC injection, if applicable, will be done after other procedures have been completed.

For a full list of study procedures, including the timing of each procedure, please refer to Section 7 and the Schedule of Assessments (Table 1).

Statistical Considerations:

General Considerations

Efficacy and safety analyses will be performed on the full analysis set (FAS), which includes all randomized subjects who have received at least 1 dose of IP. Analyses will be performed separately by dose frequency (Q2W and QM) unless specified otherwise. Methods of adjusting for multiplicity due to testing the superiority of evolocumab in combination with atorvastatin to placebo in combination with atorvastatin for both the co-primary and co-secondary efficacy endpoints within each dose frequency are provided in Section 10.5. Subject incidence of exploratory endpoint events will be summarized for each treatment group.

Analyses of Co-Primary Efficacy Endpoints

To assess the co-primary efficacy endpoints of the mean percent change from baseline at weeks 10 and 12 and percent change from baseline at week 12 in LDL-C, a repeated measures linear effects model will be used in each dose frequency to compare the efficacy of evolocumab in combination with atorvastatin and placebo in combination with atorvastatin. The repeated measures model will include terms for treatment group, stratification factors, scheduled visit and the interaction of treatment with scheduled visit. Missing values will not be imputed when the repeated measures linear effects model is used.

Analyses of Co-Secondary Efficacy Endpoints

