10.5.1 Co-primary Efficacy Endpoints

Primary analyses

To assess the co-primary endpoints, a repeated measures linear effects model will be used in each dose frequency to compare the efficacy of evolocumab in combination with atorvastatin and placebo in combination with atorvastatin in the FAS. The repeated

measures model will include terms for treatment group, stratification factors, scheduled visit and the interaction of treatment with scheduled assessment. Missing values will not be imputed when the repeated measures linear effects model is used.

The statistical significance of the treatment effect difference between evolocumab in combination with atorvastatin and placebo in combination with atorvastatin will be tested.

Multiplicity adjustment procedures are defined in Section 10.5.

Sensitivity Analysis

To evaluate the robustness of the analysis results, sensitivity analyses will be performed as follows:

- The primary analysis will be repeated using the CAS.
- Non-parametric analyses will be performed.

Subgroup Analysis

If applicable, subgroup analyses on the co-primary endpoints will be conducted using the stratification factors and baseline covariates.

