6.2 Demographics and Baseline Related Definitions

Age

Subject age at enrollment will be collected in years on the eCRF.

Baseline Lipid and Lipid-related Parameters

Baseline values for fasting lipids (total cholesterol, HDL-C, LDL-C, VLDL-C, non-HDL-C and triglycerides), ApoA1, ApoB100, ApoB48, hsCRP, Lp(a) and their derived parameters (e.g., ratio between them) are defined as the fasting concentrations

measured through central lab on Study Day 1. If for any reason a concentration for a parameter is not observed on Study Day 1, the closest prior to Study Day 1 measurement for the parameter to Study Day 1 will be used.

Body mass index (BMI)

Subject's BMI will be derived in kg/m² in the clinical database.

Other Baseline Values

For ECG data, the baseline value is defined as the nonmissing triplicate average of 3 (or all available) readings taken on Study Day 1. If the Study Day 1 reading is missing, the closest nonmissing triplicate reading prior to Study Day 1 will be used as the baseline.

For PCSK9, the baseline value is defined as the last non-missing value collected prior to or on Study Day 1, but must be prior to first IP administration.

For all other variables, the baseline value is defined as the last non-missing value collected prior to or on Study Day 1.

Change (Absolute Change) from Baseline

The arithmetic difference between a post-baseline value and baseline for a given time point:

Change (absolute change) from baseline = (post-baseline value – baseline value)

Percent Change from Baseline

The percent change from baseline for a given variable at a given time point is defined as:

[(value at a given time point – baseline value) / baseline value] x 100%

Baseline CHD Risk Factors

A subject will be categorized as having 2 or more CHD Risk Factors (Y/N) from the list of the modified NCEP ATP III risk factors:

- current cigarette smoking,
- hypertension,
- type II diabetes mellitus,
- family history of premature CHD as recorded on the eCRF, and
- low HDL-C defined as baseline HDL-C < 40 mg/dL in males and < 50 mg/dL in females.

Systematic Coronary Risk Estimation (SCORE) Categories

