10.5.1.2 Sensitivity Analyses of Co-primary Efficacy Endpoints

To evaluate the robustness of the analysis results, sensitivity analyses will be performed as follows:

- The primary analysis will be repeated using the CAS.
- Non-parametric analyses (Quade test) will be performed using the CAS.
- Multiple imputation for subjects who discontinue IP with missing endpoint data:
 - It will be assumed that the missing percent change values will be normally distributed with a mean 0 and a variance-covariance matrix the same as the observed variance-covariance matrix from subjects in the placebo group who did not discontinue IP with missing endpoint data.
 - If there is sufficient number of subjects in each treatment group who discontinue IP but have non-missing endpoint data, an additional multiple imputation will be carried out utilizing the information from these subjects to impute the missing data for subjects who discontinue IP and have missing endpoint data.

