10.5.2 Analyses of Co-secondary Efficacy Endpoints

The statistical model and testing of the tier 1 co-secondary efficacy endpoints will be similar to the primary analysis of the co-primary endpoints. The co-secondary efficacy endpoints of LDL-C target achievement as defined in Section 6.3 will be analyzed using the Cochran-Mantel-Haenszel (CMH) test adjusted by the stratification factors.

Analyses of the tier 2 co-secondary efficacy endpoints will use the same analysis model as the tier 1 endpoints, and testing will use a union-intersection test. For each tier 2 endpoint, the alternative hypothesis of the union-intersection test is that at least 1 of the treatment effects from the co-endpoints is not equal to zero.

Multiplicity adjustment procedure of testing evolocumab in combination with atorvastatin vs. placebo in combination with atorvastatin for co-secondary endpoints is defined in Section 10.1.

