10.5.3 Analyses of Tertiary Efficacy Endpoints

Analysis of the co-tertiary efficacy endpoints will be similar to the primary analysis of the primary endpoints. No multiplicity adjustment will be applied.

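### The repeated-measures model omits the endpoint's own baseline lipid value: valid, but less precise than it need be, and it over-corrects chance baseline imbalance

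*SAP*

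**What the plan says.** SAP 10.5.1.1 lists the model terms in full: "The repeated measures model will include terms for treatment group, stratification factors (from IVRS/IWRS), scheduled visit and the interaction of treatment with scheduled visit". It adds an unstructured covariance across visits. The protocol has the same terms, in section 10.5.1 ("measures model will include terms for treatment group, stratification factors, scheduled visit and the interaction of treatment with scheduled assessment") and in the synopsis ("The repeated measures model will include terms for treatment group, stratification factors, scheduled visit and the interaction of treatment with scheduled visit"). None of the three includes a baseline lipid term.

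SAP 6.2 defines baseline lipids as fasting concentrations "measured through central lab on Study Day 1", with the closest earlier value as a fallback. Percent change is computed from that value.

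The model is then carried further:

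- Tier 1: "The statistical model and testing of the tier 1 co-secondary efficacy endpoints will be similar to the primary analysis of the co-primary endpoints". The exception is LDL-C below 70 mg/dL, which uses a CMH test.
- Tier 2 uses the same model "as the tier 1 endpoints, and testing will use a union-intersection test".
- ApoA1: "Analysis of the co-tertiary efficacy endpoints will be similar to the primary analysis of the primary endpoints".

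The co-primary sensitivity analyses in SAP 10.5.1.2 are a repeat in the completer set, multiple imputation, and a rank-based test: "Non-parametric analyses (Quade test) will be performed using the CAS". No covariate is named for any of them.

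**The concern.** Change and percent change from baseline remain negatively correlated with baseline within each arm, because noise in the single Day 1 measurement enters the outcome with a negative sign. Without a baseline term, two things follow.

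First, that noise stays in the residual, so confidence intervals are wider than necessary. This also applies to the QM minus Q2W differences planned in SAP 10.1.

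Second, the change score subtracts the whole baseline difference between arms when only part of it persists to follow-up. If evolocumab happens to start higher on Day 1, it shows a spuriously larger fall (for HDL-C, a smaller rise).

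Tier 2 is where this could matter. It is confirmatory (Hochberg at 0.025 or 0.02), some of its effects may be small relative to their SD, and Hochberg steps are linked, so one p-value can change the threshold for another.

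**Working it through.** **1. The plan's own figure.** Inputs from SAP 3.2: 300 and 150 per dose frequency, 2% never dosed (294 and 147 analysed), effect 35% with SD 20%, and 15% ending IP early.

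- Attenuated effect: 0.85 × 35 = 29.75, about 30 as stated.
- Mixture SD: √(20² + 0.85 × 0.15 × 35²) = 23.6, so the stated SD of 30 is conservative.
- SE = 30 × √(1/294 + 1/147) = 3.03; z = 30/3.03 = 9.90; power above 99.99%, consistent with the stated minimum of 99%.
- 95% half-width = 1.96 × 3.03 = 5.94 points.

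**2. Direction and rough size of the precision loss.** Let r be the correlation of baseline with follow-up, with equal variances. The change score has variance 2σ²(1−r) and the baseline-adjusted outcome σ²(1−r²), a ratio of 2/(1+r): 1.54 at r = 0.3, 1.33 at 0.5 and 1.11 at 0.8. The documents do not give r. This formula ignores the strata and the percent scale, so simulation is needed.

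**3. Simulated variance ratios, unadjusted over adjusted.** Both models contain treatment, three-level entry statin (assumed to explain 20% of between-subject log variance) and three-level region; 15% are off drug with no effect. All lipid inputs are assumed:

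- LDL-C: mean 90–120 and SD 25–35 mg/dL, within-person CV 10–15%, effect 35–66%, response SD 10–20 points.
- Triglycerides: between-subject CV 30–50%, within-person 20–30%, effect 5–15%, response SD 0–20 points.
- HDL-C: between 20–28%, within 5–8%, effect 4–8%.
- Lp(a): between 90–130%, within 8–15%, effect 20–35%.

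| Endpoint | Week 12 | Mean of weeks 10 and 12 |
|---|---|---|
| LDL-C, percent | 1.01–1.17 | 1.01–1.22 |
| LDL-C, absolute | 1.04–1.30 | 1.04–1.40 |
| Triglycerides, percent | 1.05–1.27 | 1.06–1.41 |
| HDL-C, percent | 1.02–1.09 | 1.02–1.12 |
| Lp(a), percent | 1.00–1.01 | 1.00–1.02 |

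VLDL-C behaves like triglycerides if it is similarly variable. ApoA1 was not simulated. The pattern follows from r, roughly between²/(between² + within²): for triglycerides 30²/(30²+30²) = 0.50 to 50²/(50²+20²) = 0.86; for HDL-C 20²/(20²+8²) = 0.86 to 28²/(28²+5²) = 0.97.

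**4. Co-primary interval.** Scenarios whose overall SD is near 30 give ratios of only 1.02–1.07. The half-width goes from 5.94 to between 5.94/√1.07 = 5.74 and 5.94/√1.02 = 5.88. For absolute LDL-C in tier 1, z is 9–26 against a two-sided critical value of 3.38 at 0.005/7.

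**5. Validity and over-correction.** In 8,000 simulated trials per setting (294 vs 147, one visit, no strata), the unadjusted test rejected a true null in 4.9–5.5% of trials. The slope of follow-up on baseline LDL-C is 0.26–0.64 on drug and 0.59–0.92 on placebo, while the change score imposes 1. The shift from a 2-SE imbalance is pooled slope × 2 × SD(baseline) × √(1/294 + 1/147): 0.3–1.5 points for percent LDL-C and 1.5–4.3 points for percent triglycerides. Trial-level averages for triglycerides with a 10% on-drug effect:

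| CV between / within | Overall mean | Unadjusted, evolocumab 2 SE higher / lower | Adjusted, higher / lower |
|---|---|---|---|
| 30% / 30% | −9.3 | −13.6 / −5.5 | −9.7 / −9.4 |
| 50% / 20% | −8.8 | −10.3 / −7.7 | −8.9 / −9.1 |

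**6. Tier 2 power.** The SAP does not say how the union-intersection p-value is formed; a joint 2-df test is assumed. Triglycerides, 10% effect:

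| Level | Unadjusted | Adjusted |
|---|---|---|
| 0.025 | 31–83% | 35–91% |
| 0.02 | 28–81% | 32–90% |
| 0.025/4 | 16–68% | 19–81% |

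The gain at 0.025 is 3–16 points (1–7 for a 5% effect, 0–12 for 15%). A minimum-p form gives the same 3–16. A simpler one-visit run without strata gives 2–9.

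For HDL-C under the inputs in step 3, power is at least 99.8%, except at a 4% effect with 8% within-person CV (79–81% rising to 81–86%). That result depends on assuming no response SD. With a response SD of 10–15 points, unadjusted power at 0.025 is 33–99% for effects of 4–8% and adjustment adds about 0–2 points. With within-person CV of 8–12% and effects of 4–6%, it is 37–98% and the gain is about 0.5–5 points.

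**The case against.** The best defence is that nothing here is wrong. Protocol and SAP agree, the test holds its level, the estimate is unbiased over randomizations, and the co-primary endpoints have power to spare. The entry-statin stratum absorbs some baseline variation. Baseline tables by arm (SAP 10.4), co-primary subgroups by baseline LDL-C and triglycerides (SAP 7.4 and 10.5.1.3), and the optional bias-related sensitivity analyses in SAP 9.4 would make an imbalance visible. Every size above is assumed, and the gain for percent LDL-C may be as little as 1%.

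Most of that stands, and it is why the severity is low. It does not close the gap. The subgroup analyses cover only the co-primary endpoints and restore no tier 2 precision. SAP 9.4 commits to no particular model. SAP 9.6 is triggered only by failed distributional assumptions. The Quade test is limited to the co-primary endpoints in completers. Entry statin is an imperfect proxy, because baseline is measured after at least 4 weeks on atorvastatin 20 mg.

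A further objection is that the slopes differ by arm. That makes a treatment-by-baseline term an option; a common slope is sufficient here.

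A reader might also infer that the model contradicts the planned covariates in SAP 4.2, which name baseline LDL-C and triglycerides. It does not: protocol 10.1.3 and SAP 10.5.1.3 show that the list serves subgroup analyses.

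**Conclusion.** The omission and its direction are certain; the sizes are not. The plan is valid but gives away some precision and leaves an avoidable sensitivity to chance imbalance. The loss matters only for tier 2 endpoints with small effects relative to their SD: mainly triglycerides and VLDL-C, then HDL-C. ApoA1, outside the multiplicity scheme, loses some precision. Lp(a) would gain almost nothing, and the LDL-C < 70 mg/dL endpoint is untouched. The sizes rest on assumed variability, effects and response SD, and dropout-related missing data were not modelled.

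Three stronger readings are tempting and unsupported:

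- **That only triglycerides and VLDL-C can be affected.** The documents give no effect size or SD for any tier 2 lipid, and protocol 2.5 describes the HDL-C and triglyceride effects equally tentatively.
- **That the co-primary half-width could fall to about 5.5 points** (5.94/√1.17 = 5.49). The large ratios arise where the SD is near 22 and cannot be applied to an SD of 30.
- **That the −13.6 versus −5.5 contrast is typical.** It needs a 2-SE imbalance (about 5% of randomizations, both directions combined) and within-person CV equal to between-subject CV.

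**What to change.** Before unblinding:

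- Add the continuous baseline value of the analysed lipid, and its interaction with scheduled visit, to the model for the continuous tier 1, tier 2 and tertiary endpoints (SAP 10.5.2 and 10.5.3).
- For the co-primary endpoints, either add the same two terms in SAP 10.5.1.1 and keep the current model as a sensitivity analysis, or keep the protocol's model and pre-specify the baseline-adjusted one as a sensitivity analysis.
- Record the change in SAP section 11, which now reports none.
- Optionally, add a baseline-by-treatment term, and a sentence in SAP 4.2 saying that the covariate list defines subgroups.

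The cost is two model terms and a recorded departure from the model in protocol 10.5.1. No new data are needed, and no subjects should be lost, because change from baseline already requires the baseline value. Amending the protocol as well would need investigator agreement and IRB/IEC approval (protocol 12.1). Pre-specifying now also avoids an adjusted analysis being added after unblinding, when it would be post hoc.

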10.5.1.2 Sensitivity Analyses of Co-primary Efficacy Endpoints

To evaluate the robustness of the analysis results, sensitivity analyses will be performed as follows:

- The primary analysis will be repeated using the CAS.
- Non-parametric analyses (Quade test) will be performed using the CAS.
- Multiple imputation for subjects who discontinue IP with missing endpoint data:
 - It will be assumed that the missing percent change values will be normally distributed with a mean 0 and a variance-covariance matrix the same as the observed variance-covariance matrix from subjects in the placebo group who did not discontinue IP with missing endpoint data.
 - If there is sufficient number of subjects in each treatment group who discontinue IP but have non-missing endpoint data, an additional multiple imputation will be carried out utilizing the information from these subjects to impute the missing data for subjects who discontinue IP and have missing endpoint data.

